4. PROHIBITED MEDICATIONS AND TREATMENTS

During the study, patients may not use any of the medications or treatments (prescription or over the counter) listed in Table 2. If the patient begins treatment with any of the listed treatments, the patient will be disenrolled from the study with “treatment with prohibited medication” noted as reason for early discontinuation.

Table 2: Prohibited Medications and Treatments

Type of Medication or Treatment	Not Allowed During the Following Time Period
Moisturizers, creams, lotions, non-study solutions, sunscreen, and make-up on treatment areas	At any time during study
Topical steroid on treatment areas (e.g., hydrocortisone, triamcinolone)	30 days prior to screening and through End of Study – Month 6
Use of medications that suppress the immune system; for example, cyclosporine, methylprednisolone, prednisone, methotrexate, alefacept, or infliximab	30 days prior to screening and through End of Study – Month 6
Any investigational study drugs or devices	30 days prior to screening and through End of Study – Month 6

5. EVALUATION OF ADVERSE EVENTS

All adverse events and Study Device complaints will be reported on an adverse event form at each visit.

5.1. DEFINITIONS

An adverse event is an unfavorable change in health, including abnormal laboratory findings, that occurs in trial participants during the clinical trial or within a specified period following the trial. For purposes of this Protocol, the specified period is Weeks 0-24 (per patient).

An MDR reportable event is one that reasonably suggests that a marketed device has or may have caused or contributed to a death, serious injury, or has malfunctioned, and that the device or a similar device marketed by the manufacturer would be likely to cause or contribute to a death or serious injury if the malfunction were to recur. Serious Adverse Events include adverse events that result in death, require either inpatient hospitalization or the prolongation of hospitalization, are life-threatening, result in a persistent or significant disability/incapacity or result in a congenital anomaly/birth defect. Other important medical events, based upon appropriate medical judgment, may also be considered Serious Adverse Events if a trial participant's health is at risk and intervention is required to prevent an outcome mentioned.

Serious injury/(serious illness) is an injury or illness that:

- is life threatening, even if temporary in nature;
- results in permanent impairment of a body function or permanent damage to a body structure; or
- necessitates medical or surgical intervention to preclude permanent impairment of a body function or permanent damage to a body structure.

A complaint is any written, electronic or oral communication that alleges deficiencies related to the identity, quality, durability, reliability, safety, effectiveness, or performance of a device after it is released for distribution.

A malfunction is a failure of the device to meet its performance specifications or otherwise perform as intended. Performance specifications include all claims made in the labeling for the device. A reportable malfunction is a malfunction for which:

- the chance of a death or serious injury resulting from a recurrence of the malfunction is **not** remote;
- the consequences of the malfunction affect the device in a catastrophic manner that may lead to a death or serious injury;
- the malfunction causes the device to fail to perform its essential function and compromises the device's therapeutic, monitoring or diagnostic effectiveness which could cause or contribute to a death or serious injury, or other significant adverse device experiences; or
- the manufacturer takes or would be required to take action under section 518 or 519(f) of the FD&C Act as a result of the malfunction of the device or other similar devices.

Malfunctions are **not** reportable if they are not likely to result in death, serious injury or other significant adverse event experience.

Permanent impairment means irreversible impairment or damage to a body structure or function, excluding trivial impairment or damage.

Reasonably suggests includes any information, such as professional, scientific, or medical facts and observations or opinions, that would reasonably suggest that a device has caused or contributed to a reportable event.

A pre-existing condition is one that is present prior to the start of the study and is to be reported as part of the subject's medical history. It should be reported as an AE only if the frequency, intensity, or the character of the condition worsens during the study.

An unexpected AE is one not identified in nature, severity, or frequency in the current protocol.

Any clinically significant change in the study safety evaluations during treatment must be reported as an AE.

5.1.1. ADVERSE EVENT SEVERITY GRADES

The Investigator is responsible for evaluating all AEs and determining the severity of the event in a manner that enables Sponsor to submit summary AE information in connection with clinicaltrials.gov reporting. Severity will be categorized by toxicity grade according to the CTEP-CTCAE version 4.02, when applicable. AEs not found in the list of AEs described in the CTEP-CTCAE listing will be graded according to the following definitions:

Mild — Grade 1: Event may be noticeable to subject; does not influence daily activities; usually does not require intervention

Moderate — Grade 2: Event may be of sufficient severity to make subject uncomfortable; performance of daily activities may be influenced; intervention may be needed

Severe — Grade 3: Event may cause severe discomfort; usually interferes with daily activities; subject may not be able to continue in the study; treatment or other intervention usually needed

Life-Threatening — Grade 4: Event that, in the view of the Investigator, places the subject at immediate risk of death from the reaction as it occurred (i.e., it does not include a reaction that, had it occurred in a more severe form, might have caused death)

The Investigator will document AEs in all study participants consistent with the adverse events submission requirements for clinical trials registered with clinicaltrials.gov. For any AEs that are caused by or related to Microcyn™ use, and any product complaints (as defined above), the Investigator will inform Sponsor of the AE or complaint and facilitate or conduct the follow-up and information collection necessary for Sponsor to determine

the existence of a reportable MDR, i.e., an instance in which Microcyn™ caused or contributed to a participant's death or serious injury/illness.

5.1.2. STUDY PRODUCT CAUSALITY

The Study Product may have "caused or contributed" to a patient's death or serious injury, if the death or serious injury was or may have been attributed to the device, or the device may have been a factor in the death or serious injury because of:

- device failure;
- device malfunction;
- improper or inadequate device design;
- manufacture;
- labeling; or
- user error.

5.2. REPORTING ADVERSE EVENTS

The Investigator will assess subjects at each scheduled study visit for the occurrence of AEs. In order to avoid bias in eliciting AEs, subjects should be asked the following non-leading question: "How have you felt since your last visit?" All AEs (serious and non-serious) reported by the subject must be recorded on the source documents and the adverse event form.

In addition, Oculus must be notified within 24 hours of the Investigator's first knowledge of any immediately reportable events by telephone or fax by the procedure outlined below. Special attention should be paid to recording hospitalizations and concomitant therapies and medications.

5.3. IMMEDIATELY REPORTABLE EVENTS

Study Product-related deaths and serious injury/illness (reportable MDRs), as well as study participant pregnancy are considered immediately reportable events. If a subject experiences a death, serious injury/illness or pregnancy the Investigator must:

1. Report the death, injury/illness, or pregnancy by [contact]) to Oculus (refer to Appendix C – Study Responsibility List) immediately (within 24 hours) after the Investigator becomes aware of the event.

2. Complete a serious adverse event (SAE) or Pregnancy Notification Form and fax or overnight courier to Oculus within 24 hours of knowledge of the event. Note: The SAE form is NOT the AE report form.
3. Obtain and maintain all pertinent medical records, information and medical judgments of medical personnel who assisted in subject's treatment and follow-up and document on the AE report form as appropriate.
4. Provide a more detailed report to both Oculus and the IRB/IEC no later than seven (7) days after the Investigator discovers the event as further information becomes available, and when necessary update the information with follow-up information including outcomes. This report should include a statement as to whether the event was or was not related to the use of study product.
5. The Investigator will notify the IRB/IEC of the SAE or pregnancy according to specific IRB/IEC requirements.
6. The Investigator will report any device-related deaths using MedWatch Form 3500A to the FDA and the manufacturer within 10 working days, and report any serious injuries to the IRB and Sponsor.

Oculus will submit a written report to the regulatory authorities as soon as possible but no later than 15 calendar days after the initial receipt of the information regarding any serious injury or illness associated with the use of the study product.

5.4. PREGNANCY

WOCBP must consent to and receive a screening urine pregnancy test prior to study enrollment and use an effective method of birth control during the course of the study, such as the oral contraceptive pill, injection, implant, patch, vaginal ring, intrauterine coil, intrauterine device, barrier method used with an additional form of contraception (e.g., sponge, spermicide or condom), abstinence, or has a vasectomized partner. A female is considered to be of childbearing potential UNLESS she is post-menopausal (no menses for 12 consecutive months) or is without a uterus and/or both ovaries.

Before enrolling WOCBP in this clinical trial, Investigators must review guidelines about study participation for WOCBP. The topics should generally include:

Informed consent document

Pregnancy prevention information

Risks to unborn child(ren)

Any drug interactions with hormonal contraceptives

Contraceptives in current use

Guidelines for the follow-up of a reported pregnancy

Prior to study enrollment, WOCBP must undergo a screening urine pregnancy test and be advised of the importance of avoiding pregnancy during participation in this clinical study as well as the potential risk factors for an unintentional pregnancy. The subject must sign an informed consent document stating that the above-mentioned risk factors and the consequences were discussed with her.

During the study, all WOCBP should be instructed to contact the Investigator immediately if they suspect they might be pregnant (e.g., missed or late menstrual cycle). The Investigator must immediately notify Oculus of any female subject who becomes pregnant any time during study participation, record the information on the Pregnancy Notification Form and fax the form to Oculus. Oculus will ask the site to follow-up with the subject periodically during the pregnancy for ongoing health and safety information through term, as applicable. Subjects will remain on the study but will not receive re-treatment. Protocol-required procedures for the final evaluations (Month 6) evaluations must be performed for the subject unless contraindicated by pregnancy.

5.5. FOLLOW-UP OF ADVERSE EVENTS

5.5.1. FOLLOW-UP OF NON-SERIOUS ADVERSE EVENTS

Non-serious AEs that are identified during the last scheduled study visit (Month 6 or early discontinuation) must be recorded on the AE report form as ongoing.

5.5.2. FOLLOW-UP OF POST STUDY SERIOUS ADVERSE EVENTS

In the event of a reportable MDR, the Investigator should continue to report any significant follow-up information to Oculus and the IRB/IEC up to the point the event has been resolved. Resolution means the subject has returned to the Baseline state of health, or the Investigator does not expect any further improvement or worsening of the subject's condition.

Any new SAEs reported by the subject to the Investigator that occur after the last scheduled contact and are determined by the Investigator to be reasonably associated with the application of study product should be reported to Oculus and the IRB/IEC.

6. STATISTICAL ANALYSIS

6.1. GENERAL CONSIDERATIONS

All statistical programming will be performed using SAS version 9.1 or higher, or similar statistical program. Statistical significance will be based on two-sided tests at the 5% level of significance. There are two planned analyses. The first will be conducted when the greater of 20 patients or those enrolled in the two (2) weeks following enrollment of the first participant have completed the Week 12 assessments. The second will be when all 80 patients have completed the Week 24 (Final Evaluation) assessments.

6.2. POPULATIONS

All subjects will be included in the summaries of demographic and other baseline characteristics. The safety population will include all subjects ever exposed to any study product (Microcyn and saline) and have provided any post-treatment safety information. The Efficacy population will include all subjects who complete both a Baseline (Week 0) and at least one follow up visit.

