
 – Patient has any wound that at enrollment is scheduled for surgical closure within 14 days – Use of any immunosuppressant medications (for example, cyclosporine, methylprednisolone, prednisone, methotrexate, alefacept, or infliximab) within 30 days of screening – Is unable to fully comply with the study requirements; for example, if the wound is in a place that the patient cannot reach him/herself and as such requires a caregiver to apply the study product, if the patient does not have consistent twice daily access to a caregiver, this patient would be ineligible for the study – Any condition or situation which, in the Investigator’s opinion, puts the subject at significant risk, could confound the study results, or may interfere significantly with the subject’s participation in the study – Patient is medically unstable or has a life expectancy of less than 12 months – Patient is pregnant – Patient is a woman of child-bearing potential and does not consent to or receive a screening urine pregnancy test prior to study enrollment – Current enrollment in an investigational drug or device study or participation in such a study within the last 30 days prior to Baseline (Week 0) 	

Name of Sponsor/Company:	Oculus Innovative Sciences, Inc.
Name of Finished Product:	Microcyn [®] Skin and Wound Care with preservatives (“Microcyn”)
Name of Active Ingredient:	N/A
Test Article, Dose, and Mode of Administration:	
Microcyn [®] Skin and Wound Care with preservatives, applied twice daily, topical administration	
Statistical Analyses:	
Efficacy Analyses:	
Efficacy will be tested via T-tests of percent change in wound size using an intention to treat (ITT) approach as well as a per protocol analysis. Secondary analyses will include Kaplan-Meier analysis to estimate time to complete wound closure, and may include linear and logistical regression to estimate the impact of patient characteristics on study endpoints, with special emphasis on variables that affect healing times, such as diabetes and smoking status. The efficacy population will include all patients entered into the study.	
Safety Analyses:	
Safety analyses will be conducted via Fischer’s exact tests, chi-square, and t-tests, as applicable. The safety population will include all subjects exposed to the any study product (Microcyn or saline) who have provided any post-treatment safety information.	
Sample Size Justification:	

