3.2.5. DISCONTINUATION/WITHDRAWAL PROCEDURES

A subject may voluntarily withdraw from study participation at any time for any reason. If the subject withdraws consent and discontinues from the study, the Investigator will attempt to determine the reason for discontinuation and record the reason in the subject’s records. If a subject withdraws consent because of an AE, that AE should be indicated as the reason for withdrawal. In the event of early discontinuation, (i.e., prior to the earlier of complete wound closure or Week 24) and whenever possible, the subject should be asked to return to the study center to complete the final evaluations. Subjects who withdraw from the study will not be replaced.

If at any time during the study, the Investigator determines that it is not in the best interest of the subject to continue, the subject will be discontinued from participation. The Investigator can discontinue a subject at any time if medically necessary. The Investigator may discontinue a subject’s participation if the subject has failed to follow study procedures or to keep follow-up appointments. Appropriate documentation in the subject’s study record regarding the reason for discontinuation must be completed.

All subjects who fail to return to the study center for follow-up for any visit will be contacted by phone and/or email to determine the reason(s) why the subject failed to return for the necessary visit or elected to discontinue from the study. If a subject is unreachable

by telephone after a minimum of two documented attempts (one attempt on two different days), a registered letter (with duplicate sent by first class mail, postage prepaid) will be sent requesting that contact be made with the Investigator. Only after these attempts have failed will a subject be deemed lost to follow-up.

This study may be terminated in accordance with the Clinical Trial Agreement. Should this be necessary, both Oculus and the Investigator will ensure that proper study discontinuation procedures are completed.

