6.3. OVERALL STUDY EVALUATIONS AND MEASUREMENTS

6.3.1. EFFICACY

For the interim analysis, efficacy will be tested via T-tests of percent change in wound size using an intention to treat (ITT) approach as well as a per protocol analysis. For the final analysis, efficacy will be tested via T-tests of percent change in wound size using an intention to treat (ITT) approach as well as a per protocol analysis. Stratification of efficacy results by smoking status and study ulcer Stage will be conducted, although the results are expected to be similar given the stratified randomization.

For the interim analysis and final analyses, secondary analyses will include Kaplan-Meier analysis to estimate time to complete wound closure, and comparisons of infection status of the ulcer. Number and health care resource utilization (wound-related) will be tallied and compared between Microcyn and saline. Other secondary analyses may include linear and logistical regression to estimate the impact of patient characteristics on study endpoints, with special emphasis on variables that affect healing times, such as diabetes. If there are sufficient number of patients with multiple wounds, a mixed effects linear model

will be run, handling the patient as a group that has been randomized to a treatment to determine if there are any spillover effects of treating one wound with Microcyn.

If the interim analysis indicates that the difference in estimated time to complete wound closure between the two populations is 26% or higher at a significance level of $p < 0.05$, the study will be halted early for success.

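### The primary t-test is called ITT, but section 6.2 selects on attendance, disenrolment stops scheduled measurement, and no rule covers a missing Week 24 wound size

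*Combined protocol and SAP*

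**What the plan says.** **Who is analysed.** The synopsis (Statistical Analyses) says "The efficacy population will include all patients entered into the study". Section 6.2 says "The Efficacy population will include all subjects who complete both a Baseline (Week 0) and at least one follow up visit". The synopsis and section 6.3.1 both test percent change in wound size "using an intention to treat (ITT) approach as well as a per protocol analysis". Neither label is defined as a set or tied to either efficacy definition.

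**What happens to leavers.** Section 3.2.5 provides that, at early discontinuation, "whenever possible, the subject should be asked to return to the study center to complete the final evaluations". It lets the investigator discontinue a subject "if the subject has failed to follow study procedures or to keep follow-up appointments", and adds: "Subjects who withdraw from the study will not be replaced". Section 4 states: "If the patient begins treatment with any of the listed treatments, the patient will be disenrolled from the study". Table 2 lists, among others, "Moisturizers, creams, lotions, non-study solutions, sunscreen, and make-up on treatment areas". Section 3.2.2 includes lack of efficacy among the reasons for early discontinuation.

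**When the outcome is taken.** The synopsis (Study Period) defines the Final Evaluation as Week 24 or complete closure, whichever is earlier. Section 6.1 sets the final analysis for when all 80 patients have completed it. Section 6 contains no carry-forward, imputation, modelling or exclusion rule.

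**The concern.** An ITT comparison needs every randomised subject, in the arm assigned, with an outcome or a stated way of handling its absence. This plan falls short in three places.

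- The set in section 6.2 depends on attendance after randomisation and contradicts the synopsis.
- Disenrolment and discontinuation end the scheduled wound measurements, apart from one exit evaluation that may not happen. The trial is open-label, and the grounds for leaving include lack of efficacy, use of another product on the wound, and a decision by an investigator who knows the allocation. Each can be linked to arm or to healing.
- For a subject who leaves unhealed at, say, Week 8, nothing says which wound size enters the test.

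At stake is a primary result that partly rests on a choice made after the data are seen. If loss differs between arms, that choice can shift the estimate.

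**Working it through.** The plan has no figure to reproduce: 80 is a convenience sample with no effect size, SD or dropout allowance.

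**Step 1: who is affected.**
- Healed subjects and Week 24 completers: settled by the Final Evaluation definition.
- No follow-up visit: in the synopsis set, outside the section 6.2 set. They have no percent change, so the conflict matters only together with a missing-value rule.
- Left unhealed after at least one follow-up visit: in both sets, with no rule for their value. This is the larger gap.

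**Step 2: assumptions.** All of these are assumed except the total of 80 and the two-sided 5% level. Allocation is 1:1 (40 per arm) with no true difference. Percent reduction at week t = slope × t/24 + error, with slope ~ N(40, 48) and error SD 14, so the Week 24 SD is √(48² + 14²) = 50. Subjects leave after Week 4, 8 or 12, at 5% in one arm and 15% in the other.

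**Step 3: hand check.** Mean exit time is (4 + 8 + 12)/3 = 8 weeks. If loss is unrelated to healing, last value forfeits 40 × (1 − 8/24) = 26.7 points per leaver. The difference shifts by −(0.15 − 0.05) × 26.7 = −2.7. Under exclusion, leavers who are g points worse shift it by about 0.10 × g.

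**Step 4: simulation** (20,000 runs; 2,500 for multiple imputation, MI). Entries are spurious difference in points (arm with more loss minus the other), with the false-positive rate in brackets.

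| Loss, 5% v 15% | Exclude | Last value | MI within arm |
|---|---|---|---|
| Unrelated to healing | 0.0 (5.0%) | −2.7 (5.8%) | +0.1 (5.8%) |
| Recorded healing, leavers 50 points worse | +4.6 (6.8%) | −1.4 (5.3%) | +0.3 (4.4%) |
| Underlying rate, leavers 72 points worse | +6.5 (9.5%) | +0.7 (5.2%) | +3.2 (5.4%) |

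MI rates carry a simulation error of about 0.4-0.5 points. With 10% loss in both arms (the two outcome-related cases), bias is within 0.1 point for every rule. Rates are then 5.1% for exclusion, 5.1-5.2% for last value and 4.4-5.5% for MI.

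**Step 5: sensitivity to the assumptions.**
- Other selection models, exclusion: leavers about 24 points worse give 2.4 points and 5.0%; 27 worse, 2.8 and about 7%; 43 worse, 4.1 and 6.2%.
- Exits spread over Weeks 4-20 (mean 12), unrelated loss, last value: −0.10 × 40 × (1 − 12/24) = −2.0. Also capping reduction at 100% gives −1.7.
- A different model (mean Week 24 change −50%, SD 40, random loss of 10% v 30% at any visit, 4,000 runs): last value 7.5%, completers only 4.8%, 0% change assigned to all missing 19.6%. At 20% v 20%: 5.1%, 5.4% and 5.0%.

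**Step 6: the conflict between the two sets alone.** Suppose 1 v 3 of 40 have no follow-up and are 20-50 points worse. Omitting them shifts the difference by (2/40) × 20 = 1.0 to (2/40) × 50 = 2.5 points. The false-positive rate is 5.1-5.8% for SDs of 40-60.

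**Step 7: assigned values.** With 1 v 3 of 40 missing and a retained mean of 40%, assigning a reduction of a shifts the difference by (2/40)(a − 40): −4.5 for a = −50, −2.0 for a = 0, and +3.0 for a = 100. Assigning 0% is therefore not automatically conservative.

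**The case against.** The strongest reply is that the plan points toward a rule. Section 6.2 keeps anyone with one follow-up visit, which fits most naturally with using an available post-baseline value, and section 3.2.5 calls the exit assessment by the same name as the endpoint visit. That stands as implication, and it makes excluding later leavers from the ITT test the least supported reading. It is still not a rule: an exit value at Week 8 is not a Week 24 value, and no section says that it counts as one.

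A reader might go further and infer that leavers will be dropped and that the test runs near a 9.5% error rate. The documents do not support that. Section 6.2 points the other way, and the figure needs leavers 72 points worse. With a 40% overall mean, the average leaver's wound in the arm with more loss would be growing by about 21% (40 − 0.85 × 72 = −21).

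Other replies also stand in part. Section 2.4.2 requires willingness to attend all visits, and section 3.2.5 requires contact attempts. Both reduce loss but do not say how a missing value is analysed. The main simulation is crude: (100 − 40)/50 = 1.2 SD, so 11.5% of simulated subjects exceed a 100% reduction, which is impossible. The two simulation models also disagree on which rule does worse. The figures show that the rules can differ, not by how much in this trial. MI is not uniformly better: when loss follows the underlying rate, its bias (3.2) exceeds that of last value (0.7).

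**Conclusion.** The point holds on the text and should be fixed. The ITT label conflicts with the attendance condition in section 6.2 and with exits that stop scheduled outcome collection, and the value to use for an unhealed leaver is unspecified.

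The size is unknown. At an assumed 5% v 15% loss with no true difference, bias is about 0 to a few points and last value keeps the false-positive rate at about 5-6%. Higher rates at that loss arise only with exclusion and outcome-related loss, and the top of the range needs a very strong relation. A wider assumed imbalance (10% v 30%) raised last value to 7.5%. Equal loss gives about zero bias.

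A reader might infer that the contradiction between the two efficacy sets biases the result by itself. It has little effect alone, because subjects with no follow-up have no percent change to test. Nor do the documents show that loss will in fact differ between arms.

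**What to change.** 1. Make section 6.2 match the synopsis: the ITT set is all randomised subjects, analysed as randomised. Define the per-protocol set separately, with use of a listed treatment affecting only that set.
2. Reconcile sections 3.2.5 and 4 with the ITT claim, so that stopping study product or using a listed treatment does not end the wound measurements already scheduled unless consent is withdrawn. This concerns data collection only; the clinical rule is unchanged.
3. Prespecify one primary rule for a missing Week 24 value (Week 12 at the interim) that uses all available follow-up measurements, and say how an exit evaluation counts. One option is MI within arm from baseline size, Stage, smoking status and interim sizes, with a closed wound counted as 100% reduction. State that this does not fully correct loss tied to unrecorded healing or loss with no follow-up. Add last-value and assigned-value sensitivity analyses.
4. Minor: reword the section 6.1 trigger to allow for withdrawn subjects, who are not replaced. Early closure is already covered by the Final Evaluation definition.

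The cost is amendment wording, a few retained clinic visits and some analysis code. Care outside the protocol after a subject leaves study product may slightly dilute the estimate.
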